between cirrhotic patients with HE versus those without HE (27). In patients with HE, reduced levels of Lachnospiraceae, Ruminococcaceae, and Clostridiales and increased Enterobacteriaceae and Streptococcaceae closely mirror the changes caused by PPI use (25, 27). Thus, given the concordant changes in the lower GI tract microbiome seen with PPI use and in patients with HE, these bacterial taxa could play a role in mediating HE. However, other mechanisms, such as a simple effect of pH, are also plausible. Lactulose, long established as an effective treatment for HE, is a colonic acidifying agent (28). In a reduced pH environment in the colon, ammonia is protonated to the less well absorbed ammonium ion, which is thus excreted (28). By raising luminal pH, PPIs may counteract this process.

PPIs are among the most commonly used medications, but a Cochrane review has reported that 25% to 70% of patients may be prescribed a PPI inappropriately (29). Among TIPS patients, 60% to 75% take PPIs (19, 20). While short courses of PPIs are indicated for ulcer disease (30, 31) and possibly for prevention of esophageal variceal band ligation ulcers (32), PPIs do not appear in practice guidelines for prevention and management of portal hypertensive bleeding in cirrhotic patients (33). Thus, discontinuation of inessential PPI therapy in cirrhotic patients undergoing TIPS creation may be a simple and cost effective intervention to reduce the risk of post-TIPS HE.

Since the link between PPI use and HE is based solely on retrospective, observational data and because biological mechanisms remain unexplored, this protocol proposes a prospective, randomized study design to more definitively support or refute a role for PPI use as a risk factor for HE. Such a study design would more clearly determine whether discontinuation of PPI therapy can reduce the risk of post-TIPS HE and may also provide mechanistic insights into the interplay between upper GI tract pH, the GI tract microbiome, and HE.

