10.4 Description of Statistical Methods

10.4.1 General Approach

- For descriptive statistics, such as patient demographics, means and ranges will be reported for continuous variables, whereas counts and percentages will be reported for categorical variables.
- For inferential tests, differences in sample means will be assessed by two-sided unpaired T-tests, whereas differences in proportions will be assessed by two-sided Fisher's exact tests.
- For statistical mediation analysis, the non-parametric bootstrap method of Preacher and Hayes will be utilized (34).
- For all inferential tests, a two-sided p-value less than 0.05 will be considered significant.

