Here Y is a vector where the i^{th} element represents the pre to post-TIPS change in PHES for the i^{th} patient. M_j is a vector describing the bacterial abundance for the j^{th} taxon with the i^{th} element representing the pre to post-TIPS change for the i^{th} patient. X is an indicator vector where the i^{th} element is 0 if the patient was randomized to the PPI discontinuation arm and 1 otherwise. The μ and ε terms represent intercepts and error terms, respectively. Variable M_j is considered a mediator if the regression coefficients satisfy (1) $c \neq 0$, (2) $a \neq 0$, and (3) $b \neq 0$. The non-parametric bootstrap test of Preacher and Hayes will be utilized to formally test these relationships (34). For microbiome studies, the mediating effects on HE are analyzed using relative abundances of bacterial taxa at the family and genus levels in a causal compositional mediation model (43). Due to the multiplicity of bacterial families and genera, the false discovery rate will be used for multiple testing correction (44).

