10.4.11 Exploratory Analyses

Exploratory analyses related to the GI tract microbiome are described above in Section 10.4.3. These analyses are considered exploratory for the following reasons:

- To formally conclude mediation in the most rigorous sense, two additional criteria must be met in addition to those described above: (1) there can be no measurement error in the mediator variable M_j (2) Y cannot cause M_j . In this study measurement error is present in M_j , the change in abundance of the j^{th} bacterial taxon pre to post-TIPS. In addition, the pre to post-TIPS change in PHES could potentially cause changes in the GI tract microbiome, for example in patients prescribed rifaximin therapy due to overt post-TIPS HE.
- In mediation analysis, sample sizes of 50 patients are typically required to detect large effects, and medium size effects may require 100 patients (45). Therefore, the present study may lack power to detect medium size or small mediation effects.
- Because microbiome mediation analysis utilizes relative abundances of bacterial taxa at the family and genus levels (43) a multiple testing correction is required as described above. The necessity for multiple testing correction further reduces statistical power.

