10.5 Sample Size

The target sample size is estimated to provide statistical power for the primary outcome, the pre to post-TIPS change in PHES compared between the PPI continuation and discontinuation groups. Compared to pre-TIPS, patients perform approximately 18%, 51%, 26%, and 48% worse post-TIPS on the number connection A/B, digit symbol, and block design tests, respectively (46). Assuming a similar degree of PHES worsening pre- versus post-TIPS among the PPI continuation arm, but that cessation of PPIs would improve HE such that test performance is unchanged in the discontinuation arm, the estimated power with 20 patients in each arm (40 patients total) would be 71% to 96%. The proposed sample size and study duration are commensurate with previous studies. For example, previous clinical trials of lactulose and rifaximin for minimal HE randomized 61 patients for 12 weeks (47) and 42 patients for 8 weeks (48). Approximately 30 patients undergo elective TIPS creation per year at Duke University Hospital, with approximately 60-75% of those taking PPIs. Thus, approximately 20 patients per year are expected to be eligible for the study.

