10.6 Measures to Minimize Bias

10.6.1 Enrollment/Randomization/Masking Procedures

Randomization codes will be generated and maintained by the PI. Randomization of subjects between the PPI continuation and discontinuation groups will be performed in a 1:1 fashion. The patient and treating IR physician will not be blinded (open-label design). The CRC performing MHE assessments via PHES tests and QOL assessments via the CLDQ and QOLRAD surveys will be blinded to patient assignment.

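### The four families named in the rationale as possible mediators get no test of their own, so part of the power lost to multiplicity correction in the exploratory mediation analysis is avoidable

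*Combined protocol and SAP*

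**What the plan says.** Section 2.1 (Background Information) compares HE with PPI use and reports that "reduced levels of Lachnospiraceae, Ruminococcaceae, and Clostridiales and increased Enterobacteriaceae and Streptococcaceae closely mirror the changes caused by PPI use". It concludes that "these bacterial taxa could play a role in mediating HE", then adds that other mechanisms, such as a direct pH effect, are also plausible.

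Section 10.4.3 fits the mediation equations taxon by taxon at the family and genus levels. A taxon counts as a mediator if c, a and b are all non-zero. On multiplicity it says: "Due to the multiplicity of bacterial families and genera, the false discovery rate will be used for multiple testing correction". Section 10.4.9 adds that the method is Benjamini-Hochberg. Neither section mentions the taxa named in 2.1, the number of taxa to be tested, the FDR level, or whether families and genera are corrected together.

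Section 10.4.11 explains why the analysis is exploratory: 50 patients are typically needed for large mediation effects and perhaps 100 for medium ones. It adds: "The necessity for multiple testing correction further reduces statistical power". Section 10.1 says there will be no separate SAP, so these sections are the whole plan.

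**The concern.** Four families are singled out on prior evidence, and the analysis plan then treats them like any other taxon. The cost of a multiplicity correction depends on how many tests share it. Four tests need only a four-test correction; the same four placed among dozens of other taxa face a much stricter threshold. Section 10.4.11 presents the correction as a necessity. That is right for a screen of all taxa, but not for a short list fixed in advance.

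At stake is the chance of detecting a named family that truly mediates the effect, in a trial where mediation is the only stated use of the stool samples (sections 3 and 4.2.3). The choice has to be made early, because a candidate list drawn up after the sequencing results are known loses its value.

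**Working it through.** **The plan's own figure.** The only stated power, 71% to 96% in section 10.5, is for the primary outcome. No standard deviation is given, so it cannot be reproduced. Solving a two-sided t-test with 20 per arm backwards gives an implied standardised difference of 0.82 to 1.20. No power is stated for mediation.

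**Inputs from the protocol.** 40 patients, 1:1 (sections 10.5 and 10.6.1); criteria c, a and b non-zero (10.4.3); Benjamini-Hochberg (10.4.9). Section 10.4.1 says "For all inferential tests, a two-sided p-value less than 0.05 will be considered significant"; 0.05 is taken as the FDR level because none is given.

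**Assumptions.** One true mediator, independent taxa, no direct effect, and m taxa sharing the correction. With X the arm indicator (0/1) and e₁, e₂ standard normal errors:

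- M = d·X + e₁, where d is the arm difference in taxon change, in SD
- Y = b·M + e₂
- p = the larger of the a-path and b-path p-values
- detection: p < 0.05/m and p for c < 0.05

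0.05/m is the first Benjamini-Hochberg step, relevant when few taxa are true mediators. It is 0.05/4 = 0.0125 for four families and 0.05/100 = 0.0005 for 100 taxa. The joint test stands in for the planned bootstrap and compositional model.

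**Results** (40,000 simulated trials per scenario; separate runs agree within about one percentage point):

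| Scenario | Criteria | 4 families | 100 taxa |
|---|---|---|---|
| d = 1.0, b = 0.59 | a and b only | 57% | 11% |
| d = 1.0, b = 0.59 | a, b and c | 24% | 6% |
| d = 0.8, b = 0.59 | a and b only | 37% | 4% |
| d = 0.8, b = 0.59 | a, b and c | 14% | 2% |
| d = 1.2, b = 0.8 | a and b only | 85% | 39% |
| d = 1.2, b = 0.8 | a, b and c | 58–59% | 32% |

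The rows with a, b and c follow the plan's criteria.

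**If the levels are corrected separately.** With an assumed 20 to 30 families, the first scenario gives about 14% to 12% (thresholds 0.0025 and 0.0017), against 24% for four.

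**The ceiling set by c.** With no direct effect, the standardised arm difference in Y is d·b/√(1 + b²). In the first scenario this is 0.59/√1.348 = 0.51, which is significant in about 35% of trials with 20 per arm. No choice of taxon list changes that. It is smaller than the 0.82 to 1.20 implied by section 10.5. A direct effect in the same direction would raise power for c and leave the a and b tests unchanged, so the rows with a and b only are the upper limit.

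**Full Benjamini-Hochberg check.** A second simulation (4,000 trials per scenario) used 1 or 4 true mediators, arms coded ±1, equal a and b paths, and 30 to 150 taxa. With c required:

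- paths of 0.59 (arm difference 2 × 0.59 = 1.18 SD): 0.34–0.58 for four families, 0.05–0.19 for all taxa
- paths of 0.39 (arm difference 0.78 SD): 0.04–0.15 for four families, 0.003–0.02 for all taxa

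**The case against.** The strongest reply is that the plan does what it sets out to do. The formal hypothesis (section 10.2), the exploratory objective (section 3) and the exploratory endpoint (section 4.2.3) concern the microbiome in general and name no taxon. A screen of all taxa fits them. A reader might infer that the analysis abandons the trial's own hypothesis; the documents do not support that, because the named taxa appear only as background rationale, with alternatives acknowledged. This part of the reply stands.

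A reader might also infer that every family and genus goes into one pooled correction. The text does not say so. Pooling is unspecified, and separate correction by level would narrow the gap, though not close it.

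The limitation is also disclosed. Section 10.4.11 labels the analysis exploratory and says that both the sample size and the correction limit power. That stands too, and it keeps the point minor. What the disclosure misses is that, for four families already named, some of the loss is a choice.

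Finally, the simulated test is not the planned model, and real taxa are correlated and compositional. That limits the figures to direction and rough size.

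**Conclusion.** The point holds as a minor one. Giving the four named families their own correction raises power for a true mediator among them in every scenario tried: by about 18 percentage points in the first (24% versus 6%), 12 in the second (14% versus 2%) and 26–27 in the third (58–59% versus 32%), compared with correction over 100 taxa. The taxon count, effect sizes, independence and 0.05 FDR level are assumptions.

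It would be tempting to conclude that a candidate tier makes the mediation analysis adequately powered, or to cite 57% versus 11% as the gain. Neither is supported: those percentages omit the plan's own c ≠ 0 criterion, and with it the first scenario reaches only 24%. Sample size and c remain main limits. Primary and secondary conclusions are unaffected.

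**What to change.** Before any sequencing data are seen, amend sections 10.4.3 and 10.4.9 to:

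1. prespecify Lachnospiraceae, Ruminococcaceae, Enterobacteriaceae and Streptococcaceae as the first tier of candidate mediators, with their own Benjamini-Hochberg correction;
2. keep all other families and genera as a second, separately corrected, hypothesis-generating tier;
3. state the FDR level and whether families and genera are pooled.

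Optionally, add an order-level summary for Clostridiales or leave it out of the candidate rationale: it is an order, so neither planned level tests it as named.

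The cost is wording only, with the same data and essentially the same code. The downside is that two tiers must be reported and the false discovery rate is controlled within each tier rather than overall.

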10.4.4 Safety Analyses

Analyses of AEs will be performed as described above in Section 10.4.3.

10.4.5 Adherence and Retention Analyses

Analysis of on-demand acid suppression pharmacotherapy will be performed as described above in Section 10.4.3. No retention analyses are planned.

10.4.6 Baseline Descriptive Statistics

Baseline characteristics of the PPI continuation and discontinuation arms will be compared, including demographics, comorbidities, prior HE and anti-HE therapy, and TIPS procedure characteristics, using means and ranges for continuous variables and counts and percentages for categorical variables. Inferential tests to assess differences in baseline characteristics of the

groups will be performed using T-tests for continuous variables and Fisher's exact tests for categorical variables.

10.4.7 Planned Interim Analyses

10.4.7.1 Safety Review

As described above in Section 8.5 Study Halting Rules, if three SAEs related to PPI discontinuation are identified the study will be halted.

10.4.7.2 Efficacy Review

Not applicable.

10.4.8 Additional Sub-Group Analysis

Not applicable.

10.4.9 Multiple Comparison/Multiplicity

As described above in Section 10.4.3 the false discovery rate criteria of Benjamini and Hochberg (44) will be used for multiple testing correction in GI tract microbiome mediation analyses.

10.4.10 Tabulation of Individual Response Data

Not applicable.

10.4.11 Exploratory Analyses

Exploratory analyses related to the GI tract microbiome are described above in Section 10.4.3. These analyses are considered exploratory for the following reasons:

- To formally conclude mediation in the most rigorous sense, two additional criteria must be met in addition to those described above: (1) there can be no measurement error in the mediator variable M_j (2) Y cannot cause M_j . In this study measurement error is present in M_j , the change in abundance of the j^{th} bacterial taxon pre to post-TIPS. In addition, the pre to post-TIPS change in PHES could potentially cause changes in the GI tract microbiome, for example in patients prescribed rifaximin therapy due to overt post-TIPS HE.
- In mediation analysis, sample sizes of 50 patients are typically required to detect large effects, and medium size effects may require 100 patients (45). Therefore, the present study may lack power to detect medium size or small mediation effects.
- Because microbiome mediation analysis utilizes relative abundances of bacterial taxa at the family and genus levels (43) a multiple testing correction is required as described above. The necessity for multiple testing correction further reduces statistical power.

10.5 Sample Size

The target sample size is estimated to provide statistical power for the primary outcome, the pre to post-TIPS change in PHES compared between the PPI continuation and discontinuation groups. Compared to pre-TIPS, patients perform approximately 18%, 51%, 26%, and 48% worse post-TIPS on the number connection A/B, digit symbol, and block design tests, respectively (46). Assuming a similar degree of PHES worsening pre- versus post-TIPS among the PPI continuation arm, but that cessation of PPIs would improve HE such that test performance is unchanged in the discontinuation arm, the estimated power with 20 patients in each arm (40 patients total) would be 71% to 96%. The proposed sample size and study duration are commensurate with previous studies. For example, previous clinical trials of lactulose and rifaximin for minimal HE randomized 61 patients for 12 weeks (47) and 42 patients for 8 weeks (48). Approximately 30 patients undergo elective TIPS creation per year at Duke University Hospital, with approximately 60-75% of those taking PPIs. Thus, approximately 20 patients per year are expected to be eligible for the study.

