7.1 Study Procedures/Evaluations

7.1.1 Study Specific Procedures

The following will study specific procedures will occur:

- Prior to randomization, all patients will undergo assessment of MHE, using the established PHES battery of pencil-and-paper tests (Figure 3), QOL assessments using the CLDQ and QOLRAD surveys, and will be provided with return-by-mail at home stool collection kits
- Patients will be randomized to either receive instructions to immediately discontinue their PPI, or to receive no specific instructions regarding their PPI
- Patients in the PPI discontinuation arm will receive intermittent phone call reminders encouraging them to refrain from PPI use, to attempt lifestyle interventions to counteract GERD symptoms (e.g. smoking cessation, avoiding late evening meals, and head-of-the-bed elevation) (40), and to use on-demand over-the-counter histamine H2 blocker therapy for intolerable GERD symptoms
- Approximately 4 weeks following TIPS creation, all patients will undergo reassessment of MHE and QOL and will be provided with return-by-mail at home stool collection kits
- At the completion of the study, all patients will be invited to resume or discontinue PPI therapy at their discretion and upon discussion with their primary care, gastroenterology, and IR physicians

Psychometric Hepatic Encephalopathy Score

Test	Description
Number connection test A (NCT-A)	Randomly dispersed numbers are to be connected with each other in serial order as quickly as possible.
Number connection test A (NCT-B)	Randomly dispersed numbers and letters are to be connected in alternating series (1-A-2-B...) as quickly as possible.
Digit-symbol	Digits from 1 to 9 are assigned respective symbols. Under each digit the corresponding symbol is to be written within a given time.
Serial dotting	Draw a dot inside each circle as quickly as possible.
Line tracing	A given line is to be traced as quickly as possible.

Figure 3: PHES tests from (41).

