7.3.4 Final Study Visit

The final study visit will occur at the routine 4 week post-TIPS follow up IR clinic visit. Final assessments of MHE and QOL will occur and the final home stool collection kits will be provided.

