10.4.2 Analysis of the Primary Endpoint

For the primary outcome, statistical analysis will be conducted via a two-sided unpaired T-test of the hypothesis $H_0: \mu_{+PPI} = \mu_{-PPI}$ versus $H_1: \mu_{+PPI} \neq \mu_{-PPI}$. The estimate of μ_{+PPI} , the mean difference in pre versus post-TIPS PHES in the PPI continuation arm, is derived from the sample mean:

$$\bar{X}_{+PPI} = 1/n \sum (X_{post-TIPS,i} - X_{pre-TIPS,i})$$

Here $X_{post-TIPS,i}$ and $X_{pre-TIPS,i}$ are the PHES test scores 4 weeks after TIPS and 2 weeks before TIPS for i^{th} subject in the PPI continuation arm. The estimate of μ_{-PPI} is obtained in an identical fashion from patients in the PPI discontinuation arm. For the primary outcome analysis will be conducted according to the principle of ITT.

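### Section 10.5 labels 71% to 96% as power for change in PHES, but its inputs are single-test percentages that cannot give that range for one outcome with one SD, and no loss is allowed for

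*Combined protocol and SAP*

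**What the plan says.** Section 10.5 ties the calculation to the primary endpoint: "The target sample size is estimated to provide statistical power for the primary outcome, the pre to post-TIPS change in PHES". It then cites a published source for the effect: "patients perform approximately 18%, 51%, 26%, and 48% worse post-TIPS on the number connection A/B, digit symbol, and block design tests, respectively". The link to the endpoint is one clause, "Assuming a similar degree of PHES worsening pre- versus post-TIPS among the PPI continuation arm", together with the assumption that the discontinuation arm does not change. The result is "the estimated power with 20 patients in each arm (40 patients total) would be 71% to 96" per cent.

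The PHES table in section 7.1.1 lists number connection A and B, digit-symbol, serial dotting ("Draw a dot inside each circle as quickly as possible") and line tracing ("A given line is to be traced as quickly as possible"). Block design is not listed.

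Under section 10.4.2 the primary analysis is a two-sided unpaired t-test on post-TIPS minus pre-TIPS scores, which "are the PHES test scores 4 weeks after TIPS and 2 weeks before TIPS". Section 10.4.1 sets significance at two-sided 0.05. The post-TIPS score comes from one occasion: "The final study visit will occur at the routine 4 week post-TIPS follow up IR clinic visit". Section 5.4.2 foresees withdrawal after randomisation and permits replacement only of patients who withdraw before it. Section 7.5 discourages on-demand PPI use but permits it, and the primary analysis is by intention to treat. Section 10.1 says there will be no separate SAP, so section 10.5 is the whole justification.

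**The concern.** Power for a t-test on PHES change depends on the between-arm difference in PHES points divided by the SD of PHES change. Section 10.5 gives neither, and has no rule for turning a percentage on one test into PHES points. One of its four inputs is outside the battery, and serial dotting and line tracing contribute nothing.

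This is the only power figure for the primary endpoint. The comparison with earlier trials of 61 and 42 patients says nothing about power for PHES here. Section 10.4.11 warns openly of low power for the mediation analysis, but there is no similar caution for the primary endpoint. A non-significant result could therefore be read as coming from a trial with at least 71% power on PHES, which the documents do not show.

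**Working it through.** **Inputs.** 20 per arm, 1:1 (sections 10.5 and 10.6.1); two-sided 5% unpaired t-test (10.4.1, 10.4.2); worsening of 18%, 51%, 26% and 48% on the four tests in the continuation arm and none in the discontinuation arm (10.5). SD of change: not stated for PHES or for any single test.

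**1. Reproducing the plan's figure.** It cannot be computed forward without an SD, so I solved backwards. With standardised difference d, power comes from the non-central t distribution with 38 degrees of freedom and non-centrality d × √(20/2) = 3.162 d.

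- 71% power needs d = 0.816 (non-centrality 2.58).
- 96% power needs d = 1.204 (non-centrality 3.81).
- Ratio: 1.204 / 0.816 = 1.48.

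**2. Can the stated inputs give this range for PHES?** The discontinuation arm is assumed unchanged, so the between-arm difference equals the worsening in the continuation arm. If PHES worsens by w per cent and PHES change has SD s on the same scale, then d = w / s. With one s, the ratio of d values must equal the ratio of percentages: 51 / 18 = 2.83, not 1.48. Dropping block design (48%) leaves both extremes, and so the ratio, unchanged.

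- Set s so that 51% gives 96%: 18% then gives d = 1.204 × 18/51 = 0.425, power 26%.
- Set s so that 18% gives 71%: 51% then gives d = 0.816 × 51/18 = 2.31, power above 99.9%. In this case 26% gives d = 0.816 × 26/18 = 1.18, power 95%. The two smaller percentages alone would come close to the range, but section 10.5 lists all four.

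**3. What would produce 71% to 96%?** For both extreme tests to fall inside the range, the SD must lie between 51/1.204 = 42 and 51/0.816 = 62 percentage points for the 51% test, and between 18/1.204 = 15 and 18/0.816 = 22 for the 18% test. The intervals do not overlap; the SDs must differ at least 1.9-fold (42.3 / 22.1). Separate SDs for separate tests could do this. One SD for PHES change cannot.

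**4. Loss of patients (assumed rates, equal in both arms).** The change score needs both visits. Holding d at 0.816 and 1.204:

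| Evaluable | Per arm | Power |
|---|---|---|
| 40 (no loss) | 20 | 71% to 96% |
| 36 (10% loss) | 18 | 66% to 94% |
| 32 (20% loss) | 16 | 61% to 91% |

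**5. What can be stated without a PHES SD.** The difference detectable with 80% power, and the expected half-width of the 95% confidence interval, t × √(2/n), both in SDs of PHES change:

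| Evaluable | 80% power at | Half-width |
|---|---|---|
| 40 | 0.91 | 2.024 × √(2/20) = 0.64 |
| 36 | 0.96 | 2.032 × √(2/18) = 0.68 |
| 32 | 1.02 | 2.042 × √(2/16) = 0.72 |

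**The case against.** The best defence is that the plan never says the four tests share an SD. They are scored differently (some by time, digit-symbol by symbols written in a set time), and the cited source may hold test-specific SDs that reproduce 71% and 96% exactly. Three of the four inputs are PHES components, the bridge to PHES is stated openly as an assumption, and the lower limit below 80% is not hidden.

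Much of this stands. A reader might infer that the range is a calculation error, or that true power is 26%. The documents support neither: the 26% follows only from imposing one SD on all the percentages, and the original calculation may be correct test by test. The assumption of complete protection in the discontinuation arm is also disclosed, and I do not contest it.

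The defence does not rescue the label. Section 10.5 claims power for change in PHES, which is one outcome with one SD. If separate SDs lie behind the range, it is power for single tests, and the assumption of a similar degree of worsening does not convert it.

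On loss and crossover, no rates are in the documents, and the reminder contacts and routine four-week visit may keep both low. The loss figures are therefore illustrations. A reader might also want a crossover-adjusted power. On-demand PPI use under intention to treat would tend to lower power, but the documents do not allow the amount to be estimated.

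**Conclusion.** The statement is wrong as written and should be fixed. The range of 71% to 96% is not power for the primary endpoint on any reading that uses all the stated inputs with one SD for PHES change; at best it is single-test power carrying the wrong label. The ratio check (1.48 against 2.83) depends only on the test, the sample size, the listed percentages and the disclosed no-change assumption.

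The documents do not show that the trial is underpowered for PHES. Power on that scale is unknown, because neither the difference nor the SD is given. At least 71% power holds only if the true difference is 0.82 SD of PHES change or more and all 40 patients are evaluable. The loss-adjusted ranges rest on assumed rates and on d values taken back from the plan's own figure.

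**What to change.** Change the text of section 10.5 only.

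1. Stop presenting 71% to 96% as power for change in PHES. If it is kept, label it as single-test power and name the test and SD behind each figure. Drop block design as a basis.
2. For PHES, give a point difference and an SD of change with their source, and recompute with a stated allowance for loss.
3. If no source exists, say so and state: with 40 randomised, the two-sided 5% t-test has 80% power for a between-arm difference of 0.91 SD of PHES change if all 40 are evaluable, 0.96 SD if 36 are and 1.02 SD if 32 are, with 95% confidence interval half-widths of about 0.64, 0.68 and 0.72 SD; power is lower with crossover; and a non-significant result will be read from its 95% confidence interval.
4. Mark any loss or crossover figure as an assumption.

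Sample size, test and conduct do not change. The costs are a less favourable power statement, a search for a PHES SD, and a small interpretive commitment: sections 10.4.1 and 10.4.2 now specify tests and p-values, not interval-based reading of a null result.
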